4.1 Screening, Enrollment, and Randomization

The study investigators will identify patients with an ABI of ≤ 0.9 , screen these patients for eligibility, and notify the physician(s) of any eligible patient(s). The physician(s) will inform the eligible patient(s) about the study and ask the patient(s) for permission to have the study investigators meet the patient(s) at their next clinic visit. The study investigators will meet with these patients; discuss the study objective, process, benefits, risks, and alternatives; and obtain written informed consent and HIPAA authorization. Once the patients have provided written informed consent and HIPAA authorization, they will be enrolled into the study and randomized.

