4.2.2 Fitness Monitor

Both the control group and the intervention group will receive a Fitbit Flex which has been validated for step count measurement. During enrollment, the study investigators will set up the Fitbit Flex for all patients. This set-up process will be the only stage where patients will need to have online access. In order to set up the Fitbit Flex, all patients will need to have a mobile phone with WiFi and Bluetooth capability. The study investigators will download the free Fitbit application onto the mobile phone for each patient, create a free online Fitbit account for each patient, and pair the Fitbit Flex to the mobile application. Once the Fitbit Flex and the mobile application are paired, the Fitbit Flex can sync data to the online Fitbit account wirelessly through Bluetooth. Patients will be instructed to sync their Fitbit data to their online Fitbit account every 4 weeks.

The study investigators will have access to all online Fitbit accounts for the study duration (3 months for the primary and secondary endpoints, and 1 year for the exploratory endpoints). There will be no patient-identifying information in any online Fitbit account. Instead, each patient will be assigned a random alphanumeric code, which will be used as the patient name on the online Fitbit account.

At the end of the study, all patients will be allowed to keep their Fitbits at no cost, indefinitely.

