5.1 Baseline Assessment Period

Week 1 will be the baseline assessment period, during which both the intervention group and the control group will wear their fitness monitors for 7 consecutive days. In addition to their usual daily activities, all patients will be instructed to walk continuously for at least one extended period of time on a daily basis. Given that this is a pilot study of a novel exercise program in PAD patients, the duration and frequency of these extended periods of time will be at the patients' discretion.

At the end of Week 1: the study investigators will conduct both chart review and phone calls for all enrolled patients to assess for any drop-out criteria and adverse events. In addition, the study investigators will instruct patients regarding any concerning symptoms that should be reported to the study team or should require emergent medical attention (by calling 911). Both groups will transmit the data from their fitness monitors to their online Fitbit accounts. Finally, both groups will also complete quality of life surveys (PAQ and VascuQol).

Prior to starting the Week 1 baseline assessment period, patients who undergo peripheral angiography will need to be cleared for full activity by the treating interventional cardiologist. The study investigators will ask the patients' treating interventional cardiologist 1 week after the procedure to verify the patients' clearance for full activity, and then call the patients with instructions to start the Week 1 run-in period.

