5.2 Endpoint Assessment Period

Week 14 will be the endpoint assessment period and will be structured identically to Week 1, during which both the intervention group and the control group will wear their fitness monitors for 7 consecutive days. In addition to their usual daily activities, all patients will be instructed to walk continuously for at least one extended period of time on a daily basis. Given that this is a pilot study of a novel exercise program in PAD patients, the duration and frequency of these extended periods of time will be at the patients' discretion.

At the end of Week 14: the study investigators will conduct both chart review and phone calls for all enrolled patients to assess for any drop-out criteria and adverse events. In addition, the study investigators will instruct patients regarding any concerning symptoms that should be reported to the study team or should require emergent medical attention (by calling 911). Both groups will transmit the data from their fitness monitors to their online Fitbit accounts. Finally, both groups will also complete quality of life surveys (PAQ and VascuQol).

6. Statistical Analysis

The primary endpoint of the mean daily walking distance (in steps) over 7 consecutive days will be assessed at baseline and at 3 months. Mean improvement in steps walked from baseline to 3 months will be calculated separately for the intervention and the control group. Noninferiority of the intervention group will be assessed by comparing mean improvement in steps walked, using a 1-sided t-test with a margin of noninferiority of 500 steps. Pedometry data from 22 patients with coronary artery disease undergoing 4 month behavioral intervention suggests the mean improvement in steps walked will have a standard deviation of 161 (VanWormer J, Boucher J, Pronk N, Thoennes J. Lifestyle behavior change and coronary artery disease: effectiveness of a telephone-based counseling program. *J Nutr Educ Behav*. 2004 Nov-Dec; 36(6):333-4.). With a sample size of 20 patients per group, we expect 90% power to demonstrate noninferiority of the intervention group (difference in mean improvement of -350 steps, which is within the margin of noninferiority).

The mean difference in the mean daily walking distance between the study groups will be analyzed by multiple linear regression, controlling for baseline mean daily walking distances. All outcomes will be analyzed by intention-to-treat.

7. Data Management

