9.1 Study Flow Diagram

9.2 **Control Group: Symptom-based Exercise Protocol**⁶⁻⁸

Week	Exact Dates *	Frequency	Exercise Prescription
1	(Run-in period)	Daily	Walk as much as possible
2		3-5 days a week	1. Walk on a flat surface at a constant speed for 45 consecutive minutes
3		3-5 days a week	2. Rest when you have leg pain (3 or 4 on a pain scale between 1 and 5, where 1 is no pain and 5 is severe pain)
4		3-5 days a week	3. Start walking when your leg pain has stopped
5		3-5 days a week	4. Repeat these walking/rest cycles
6		3-5 days a week	5. If you are able to walk for 8 minutes without stopping, increase your walking speed.
7		3-5 days a week	
8		3-5 days a week	
9		3-5 days a week	
10		3-5 days a week	
11		3-5 days a week	
12		3-5 days a week	
13		3-5 days a week	
14	(Endpoint period)	Daily	Walk as much as possible

* The exact dates will be written on the exercise prescription for each patient.

9.3 **Intervention Group: Step-based Exercise Protocol**

Week	Exact Dates *	Frequency	Exercise Prescription
1	(Run-in period)	Daily	Walk as much as possible
2		Daily	Walk at least 3,000 steps
3		Daily	Walk at least 3,500 steps
4		Daily	Walk at least 4,000 steps
5		Daily	Walk at least 4,500 steps
6		Daily	Walk at least 5,000 steps
7		Daily	Walk at least 5,000 steps
8		Daily	Walk at least 5,000 steps
9		Daily	Walk at least 5,000 steps
10		Daily	Walk at least 5,000 steps
11		Daily	Walk at least 5,000 steps
12		Daily	Walk at least 5,000 steps
13		Daily	Walk at least 5,000 steps
14	(Endpoint period)	Daily	Walk as much as possible

* The exact dates will be written on the exercise prescription for each patient.

10. References

3. McDermott MM. Lower extremity manifestations of peripheral artery disease: the pathophysiologic and functional implications of leg ischemia. *Circ Res*. 2015;116(9):1540-1550.

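### Randomization at consent precedes the Week 1 baseline, so baseline steps and surveys can depend on the assigned arm

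*Combined protocol and SAP*

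**What the plan says.** Section 4.1 fixes the moment of allocation: "Once the patients have provided written informed consent and HIPAA authorization, they will be enrolled into the study and randomized". Section 4.2.2 adds "During enrollment, the study investigators will set up the Fitbit Flex for all patients", a step that is the same in both arms.

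Section 5.1 then describes the baseline: "Week 1 will be the baseline assessment period, during which both the intervention group and the control group will wear their fitness monitors". Patients are asked to add at least one continuous walk a day, but "the duration and frequency of these extended periods of time will be at the patients' discretion". The end of Week 1 brings a phone call, a chart review for drop-out criteria and adverse events, data transmission, and completion of the PAQ and VascuQol by both groups.

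The Week 1 row appears in each arm's own prescription table (Sections 9.2 and 9.3), with the footnote "The exact dates will be written on the exercise prescription for each patient". In Section 9.3 the step targets for Weeks 2 to 13 stand directly below that row.

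Section 6 uses the baseline twice. For the primary test, "Mean improvement in steps walked from baseline to 3 months will be calculated separately for the intervention and the control group", and the two means are compared by a one-sided t-test. The difference between groups is also to be analyzed by "multiple linear regression, controlling for baseline mean daily walking distances". All outcomes are analyzed by intention-to-treat.

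**The concern.** A baseline is protected by randomization only if it is fixed before allocation, or if allocation cannot influence it. Neither is assured here. The measure is a behavior that the patient controls, recorded on a device the patient wears, after assignment. Only one arm is given a step target. A patient who already holds the step-based sheet has a reason to treat the Week 1 count differently from a patient holding the symptom-based sheet.

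The direction matters:

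- If knowing the arm raises Week 1 steps in the step-based arm, that arm's improvement is understated and true non-inferiority may be missed.
- If it raises Week 1 steps in the control arm, or lowers them in the step-based arm, the comparison is tilted toward a false non-inferiority claim.

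The change in PAQ and VascuQol also rests on a baseline taken after allocation. The plan gives no margin for these, so no size is put on that part.

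There is a second consequence. The end-of-Week-1 check can discontinue a patient who has already been randomized. That patient counts under intention-to-treat without having started either program.

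**Working it through.** **Order of events.** Consent, then randomization (4.1); Fitbit set-up during enrollment (4.2.2); Week 1 steps, then the surveys and drop-out check at the end of Week 1 (5.1); programs in Weeks 2 to 13 (4.3). Every baseline value is recorded after allocation.

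**Inputs from Section 6.** Margin 500 steps; expected difference -350; SD of improvement 161; 20 per group; one-sided t-test; stated power 90%. Alpha is not stated.

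**Reproducing the plan's power.**

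- SE = 161 × √(2/20) = 50.9 steps, with 38 degrees of freedom.
- Distance from the expected difference to the margin = 500 - 350 = 150 steps, so the noncentrality is 150/50.9 = 2.95.
- Noncentral t power: 89.4% at one-sided 0.05 and 81.9% at one-sided 0.025.

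One-sided 0.05 matches the stated 90% and is assumed below, with 0.025 alongside.

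**Effect of a baseline shift on the t-test.** Let b be the difference between arms in Week 1 steps that is caused by allocation. The documents give no value, so b is assumed. The estimated difference in improvement moves by b.

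- Step-arm baseline higher: power = P(T > t-critical), noncentrality (150 - b)/50.9.
- Control baseline higher, true difference -500: false-claim rate = P(T > t-critical), noncentrality b/50.9.

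| Assumed b (steps) | Power, 0.05 | False claim, 0.05 | Power, 0.025 | False claim, 0.025 |
|---|---|---|---|---|
| 0 | 89.4% | 5.0% | 81.9% | 2.5% |
| 25 | 77.8% | 12.3% | 66.7% | 6.9% |
| 50 | 61.2% | 24.8% | 48.2% | 15.8% |
| 100 | 24.8% | 61.2% | 15.8% | 48.2% |

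**Sensitivity to the SD.** At one-sided 0.05 with b = 50:

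- SD 500 (assumed): false claim 9.1%; power falls from 23.8% to 15.3%.
- SD 1,000 (assumed): false claim 6.8%; power falls from 11.9% to 9.1%.

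**Regression on baseline.** The covariate is itself recorded after allocation, so adjustment leaves a bias of about slope × b. This was simulated at one-sided 0.05 with b = 50 added to the recorded baseline only. SDs were equal at both times and scaled so that the SD of change is 161. That scaling implies a between-patient SD of 161/√(2(1 - slope)), which is 136, 161, 208 and 360 steps for the four slopes.

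| Assumed slope | Bias (steps) | False claim | Power without and with shift |
|---|---|---|---|
| 0.3 | 15 | 10% | 97% to 93% |
| 0.5 | 25 | 13% | 95% to 86% |
| 0.7 | 35 | 18% | 93% to 76% |
| 0.9 | 45 | 22% | 90% to 66% |

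Adjustment shrinks the distortion but does not remove it.

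**The case against.** The causal link is inferred. Harm requires that patients know their arm during Week 1 and walk differently because of it, and the text states neither. The time at which the sheets are handed over is not given, and the flow diagram (9.1) is not in the text available for review. For patients having angiography, Week 1 starts only after clearance and a later call, so their dated sheet may not exist at enrollment. This stands: the order of events is certain, but the presence of bias is not.

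The safeguards are real. Both arms receive the same Week 1 instruction and the same monitor, and the step targets begin only in Week 2. These reduce the risk. They do not remove it, because the amount of walking stays with the patient.

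Week 14 has the same structure as Week 1 and is also open-label, so an effect of arm knowledge present in both weeks would cancel in the change score. If half persisted, a 50-step shift would act like 25, and the false-claim rate would be 12% rather than 25%. The tables should therefore be read as the case with no counterpart in Week 14. The point does not settle the matter, since nothing ensures that the two effects are equal, and a baseline shift caused by allocation is still subtracted from the Week 14 difference.

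The large percentages depend on the SD of 161. This also stands, and the larger-SD results belong beside them. Finally, the Week 1 drop-out argument covers a single week, and the documents give no rate for it.

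**Conclusion.** The concern holds and should be fixed. As written, the plan records every baseline value for the primary and secondary endpoints after allocation, with no described withholding of the arm, and so allows baseline to depend on the arm. The documents do not show that it will.

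The size is illustrative. The plan leaves 150 steps between its expected difference and its margin, and at its own SD a shift of 25 to 50 steps is enough to change the operating characteristics materially. At the larger assumed SDs the same shift matters much less, although power is then already poor. The figures rest on assumed shifts and slopes, an assumed alpha, and no offsetting effect in Week 14. Confidence is high on the sequence and on the value of correcting it; the direction and size of any actual bias are unknown.

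**What to change.** Amend Sections 4.1 and 5.1 so that the order is:

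1. Obtain consent and set up the Fitbit.
2. Record Week 1, sync the steps, and collect the PAQ and VascuQol.
3. Complete the end-of-Week-1 drop-out check.
4. Randomize at that same contact, and only then disclose the arm and issue the arm-specific sheet.

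Move the Week 1 row out of Sections 9.2 and 9.3 onto one sheet common to all patients. Say how the surveys are returned and how the dated sheet reaches the patient before Week 2, since this contact is by phone.

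The minimum alternative is to keep randomization where it is and state that the arm is withheld from patients until the end-of-Week-1 contact. That protects the baseline, but Week 1 losses would still fall after randomization.

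The cost is an IRB amendment and allocation by phone rather than in clinic. Slightly more than 40 patients may need to consent, and a few Fitbits may go to patients who are never randomized; the minimum alternative avoids these last two. No visit or measurement is added, and with 20 per group randomized after Week 1 the planned power is unchanged. Neither option masks Week 14, which remains open-label.

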4.2 Treatment

4.2.1 Standard Medical Therapy

Both the control group and the intervention group will receive standard medical therapy: lipid-lowering therapy; antiplatelet therapy with aspirin 81mg daily or clopidogrel 75mg daily; anti-hypertensive therapy for patients with hypertension; and smoking cessation therapy^{7,8}. Given that all these medical therapies are the standard of care for PAD patients, these medications will be initiated and/or managed by the usual care provider. The study team will only provide advice about the standard of care.

4.2.2 Fitness Monitor

Both the control group and the intervention group will receive a Fitbit Flex which has been validated for step count measurement. During enrollment, the study investigators will set up the Fitbit Flex for all patients. This set-up process will be the only stage where patients will need to have online access. In order to set up the Fitbit Flex, all patients will need to have a mobile phone with WiFi and Bluetooth capability. The study investigators will download the free Fitbit application onto the mobile phone for each patient, create a free online Fitbit account for each patient, and pair the Fitbit Flex to the mobile application. Once the Fitbit Flex and the mobile application are paired, the Fitbit Flex can sync data to the online Fitbit account wirelessly through Bluetooth. Patients will be instructed to sync their Fitbit data to their online Fitbit account every 4 weeks.

The study investigators will have access to all online Fitbit accounts for the study duration (3 months for the primary and secondary endpoints, and 1 year for the exploratory endpoints). There will be no patient-identifying information in any online Fitbit account. Instead, each patient will be assigned a random alphanumeric code, which will be used as the patient name on the online Fitbit account.

At the end of the study, all patients will be allowed to keep their Fitbits at no cost, indefinitely.

4.2.3 Control Group

The control group will receive the following 12-week symptom-based exercise prescription, which is adapted from clinical practice guidelines⁵⁻⁸.

- Walk on a flat surface at a constant speed until there is mild to moderate pain
- Rest until the pain has completely ceased
- Resume walking at the same speed
- Increase the speed when you can walk 8 minutes without stopping for leg symptoms
- Continue this exercise routine for 45 consecutive minutes, 3 to 5 days a week.

4.2.4 Intervention Group

The intervention group will receive the following 12-week step-based exercise prescription. The exercise goal of 5,000 daily steps is based on prior evidence demonstrating that a daily step count of less than 5,000 is associated with a negative impact on health²⁶.

- Week 1: walk at least 3,000 steps every day.
- Week 2: walk at least 3,500 steps every day.
- Week 3: walk at least 4,000 steps every day.
- Week 4: walk at least 4,500 steps every day.
- Weeks 5-12: walk at least 5,000 steps every day.

4.3 **Follow-up**

The study follow-up period will be 14 weeks. Week 1 will be a baseline assessment period during which we obtain baseline data. Weeks 2 through 13 will be the period of the study intervention. Week 14 will be the endpoint assessment period during which we obtain endpoint data.

Week 1

Discussed in Section 5.1 (Study Assessments, Baseline Assessment Period)

Weeks 2 to 13

Every 4 weeks of the 12-week exercise program: the study investigators will conduct both chart review and phone calls for all enrolled patients to assess for any drop-out criteria and adverse events. In addition, the study investigators will instruct patients regarding any concerning symptoms that should be reported to the study team or should require emergent medical attention (by calling 911). In order to assess compliance to the study protocol, all patients will transmit data from their fitness monitors to their online Fitbit accounts every 4 weeks.

Week 14

Discussed in Section 5.2 (Study Assessments, Endpoint Assessment Period)

5. Study Assessments

5.1 Baseline Assessment Period

Week 1 will be the baseline assessment period, during which both the intervention group and the control group will wear their fitness monitors for 7 consecutive days. In addition to their usual daily activities, all patients will be instructed to walk continuously for at least one extended period of time on a daily basis. Given that this is a pilot study of a novel exercise program in PAD patients, the duration and frequency of these extended periods of time will be at the patients' discretion.

At the end of Week 1: the study investigators will conduct both chart review and phone calls for all enrolled patients to assess for any drop-out criteria and adverse events. In addition, the study investigators will instruct patients regarding any concerning symptoms that should be reported to the study team or should require emergent medical attention (by calling 911). Both groups will transmit the data from their fitness monitors to their online Fitbit accounts. Finally, both groups will also complete quality of life surveys (PAQ and VascuQol).

Prior to starting the Week 1 baseline assessment period, patients who undergo peripheral angiography will need to be cleared for full activity by the treating interventional cardiologist. The study investigators will ask the patients' treating interventional cardiologist 1 week after the procedure to verify the patients' clearance for full activity, and then call the patients with instructions to start the Week 1 run-in period.

5.2 Endpoint Assessment Period

Week 14 will be the endpoint assessment period and will be structured identically to Week 1, during which both the intervention group and the control group will wear their fitness monitors for 7 consecutive days. In addition to their usual daily activities, all patients will be instructed to walk continuously for at least one extended period of time on a daily basis. Given that this is a pilot study of a novel exercise program in PAD patients, the duration and frequency of these extended periods of time will be at the patients' discretion.

At the end of Week 14: the study investigators will conduct both chart review and phone calls for all enrolled patients to assess for any drop-out criteria and adverse events. In addition, the study investigators will instruct patients regarding any concerning symptoms that should be reported to the study team or should require emergent medical attention (by calling 911). Both groups will transmit the data from their fitness monitors to their online Fitbit accounts. Finally, both groups will also complete quality of life surveys (PAQ and VascuQol).

6. Statistical Analysis

The primary endpoint of the mean daily walking distance (in steps) over 7 consecutive days will be assessed at baseline and at 3 months. Mean improvement in steps walked from baseline to 3 months will be calculated separately for the intervention and the control group. Noninferiority of the intervention group will be assessed by comparing mean improvement in steps walked, using a 1-sided t-test with a margin of noninferiority of 500 steps. Pedometry data from 22 patients with coronary artery disease undergoing 4 month behavioral intervention suggests the mean improvement in steps walked will have a standard deviation of 161 (VanWormer J, Boucher J, Pronk N, Thoennes J. Lifestyle behavior change and coronary artery disease: effectiveness of a telephone-based counseling program. *J Nutr Educ Behav*. 2004 Nov-Dec; 36(6):333-4.). With a sample size of 20 patients per group, we expect 90% power to demonstrate noninferiority of the intervention group (difference in mean improvement of -350 steps, which is within the margin of noninferiority).

The mean difference in the mean daily walking distance between the study groups will be analyzed by multiple linear regression, controlling for baseline mean daily walking distances. All outcomes will be analyzed by intention-to-treat.

7. Data Management

In order to protect patient confidentiality, we will abide by the following policies for data management.

All paper data will be stored in a study binder that will be stored and locked in a locker. Only the study personnel listed on this IRB protocol will have access to the study binder, and the key to the locker for the study binder.

All electronic data will be stored in an online project database which is a secured web-based application. Only the study personnel listed on this IRB protocol will be authorized users for the project database, and will have access to the project database.

We will use online randomization software to generate a random numeric code for each patient. Patient identifying data (specifically name, date of birth, medical record number, telephone number, and Fitbit serial number) will be stored only as electronic data on a single form in the online project database. The random numeric code for each patient will be documented on this single form with the patient identifying data. This single form will be the key to the random numeric codes, and will be stored separately from the research data. Only the study personnel listed on this IRB protocol will have access to this key. The rest of the online forms will use the random numeric codes to identify patients. All paper forms will use the random numeric codes to identify patients. All online Fitbit accounts will use the random numeric codes to identify patients.

Only the individuals listed on the IRB protocol will have access to any study data (the study binder in the locker, the online Fitbit accounts, and the study database).

At the completion of the data analysis, all online data will be destroyed and all paper data will be disposed in the HIPAA-protected waste bins.

8. Study Conduct

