1.4 Study Funding

In August 2016, we were awarded an NC TraCS Pilot Grant (#2KR821606) for the execution of this study.

2. **Study Objectives**

2.1 **Primary Endpoint**

The primary endpoint will be the change in the mean daily walking distance over 7 consecutive days between baseline (prior to the exercise program) and after 12 weeks of the exercise program.

2.2 **Secondary Endpoints**

The secondary endpoint will be the change in quality of life between baseline (prior to the exercise program) and after 12 weeks of the exercise program. We will assess quality of life with 2 surveys that have been validated in PAD patients: the Peripheral Artery Questionnaire (PAQ) and the Vascular Quality of Life Questionnaire (VascuQol).

2.3 **Safety Endpoints**

The safety endpoint will be the occurrence of physical injury, myocardial infarction, or sudden cardiac death at 12 weeks.

3. Study Population

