3.1 Inclusion Criteria

Patients are eligible for enrollment if they meet all of the following criteria.

1. Male or female with an age of 18 years or older
2. Diagnosis of lower extremity PAD, based on at least 1 of the following criteria:
 - Ankle-brachial index (ABI) of 0.9 or less in one or both legs
 - Invasive angiography demonstrating obstructive lower extremity artery disease
 - History of prior endovascular or surgical revascularization of lower extremity artery
3. Symptomatic lower extremity PAD characterized by:
 - Fontaine Stage IIa - intermittent claudication after walking > 200 meters
 - Fontaine Stage IIb - intermittent claudication after walking < 200 meters
4. Have a mobile phone with Wifi and Bluetooth capability
5. Have a safe and suitable walking environment (e.g. safe sidewalks next to home)
6. Have the ability to read and speak the English language

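### Non-inferiority rests on an unadjusted t-test on change, while the baseline-adjusted regression of the same contrast, already planned in Section 6, has no margin and no role

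*Combined protocol and SAP*

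**What the plan says.** Section 2.1: "The primary endpoint will be the change in the mean daily walking distance over 7 consecutive days between baseline" and the end of the 12-week program.

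Section 6, first paragraph, names the deciding test: "Noninferiority of the intervention group will be assessed by comparing mean improvement in steps walked, using a 1-sided t-test". The 500-step margin is attached to that test. The paragraph takes the variability from pedometry data in 22 coronary patients, which "suggests the mean improvement in steps walked will have a standard deviation of 161", and assumes a true difference of -350 steps. It then states: "With a sample size of 20 patients per group, we expect 90% power to demonstrate noninferiority of the intervention group".

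Section 6, second paragraph, says that the mean difference between groups in mean daily walking distance "will be analyzed by multiple linear regression, controlling for baseline mean daily walking distances". No margin, hypothesis or confidence limit is attached to this model, and it is not called primary, supportive or sensitivity. Alpha is not stated for either analysis. Nothing says which result governs if the two disagree.

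**The concern.** The two paragraphs address one quantity. Once baseline steps are in the model, the arm coefficient is identical whether the response is Week 14 steps or change from baseline: subtracting baseline from the response lowers the baseline slope by exactly 1 and leaves the arm term alone. The regression is therefore a second estimate of the non-inferiority contrast, yet as written it cannot decide non-inferiority.

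Two things are at stake. The change-score test fixes the baseline slope at 1 instead of estimating it, which can waste precision and leaves part of any chance baseline imbalance in the estimate. And having two analyses of one contrast, only one with a decision rule, leaves open how a disagreement would be reported.

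**Working it through.** **Inputs from Section 6.** Margin 500 steps; true difference -350, so the distance to the margin is 500 - 350 = 150; SD of change 161; n = 20 per arm; one-sided test.

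**Inputs assumed.** Alpha (0.05 and 0.025 both tried), the baseline SD (σ) and the correlation between baseline and Week 14 steps (ρ). None is in the documents.

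**1. The plan's own figure.** SE = 161 × √(2/20) = 50.9, so the noncentrality is 150/50.9 = 2.946 on 38 df.
- One-sided 0.05: power 89.4% (noncentral t) or 90.3% (normal approximation). The stated 90% reproduces.
- One-sided 0.025: 81.9% or 83.8%. It does not reproduce.

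The power statement therefore implies one-sided 0.05.

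**2. Variance of the two analyses.** With equal variances at both times:
- change score: 2σ²(1 - ρ)
- baseline-adjusted residual: σ²(1 - ρ²)
- ratio, adjusted to change: (1 + ρ)/2

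Holding the change SD at 161 forces σ = 161/√(2(1 - ρ)). Adjusted power uses 37 df and is averaged over chance baseline imbalance.

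| ρ | implied baseline SD | residual SD | adjusted power, 0.05 | adjusted power, 0.025 |
|---|---|---|---|---|
| 0.3 | 136 | 129.8 | 97.1% | 93.9% |
| 0.5 | 161 | 139.4 | 95.0% | 90.4% |
| 0.7 | 208 | 148.4 | 92.6% | 86.6% |
| 0.9 | 360 | 156.9 | 90.0% | 82.7% |
| t-test | – | – | 89.4% | 81.9% |

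**3. The same, indexed by baseline SD** (change SD 161, one-sided 0.05):

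| baseline SD | 150 | 200 | 300 | 400 | 480 | 500 | 750 | 1,000 |
|---|---|---|---|---|---|---|---|---|
| adjusted power, % | 95.9 | 92.9 | 90.6 | 89.7 | 89.4 | 89.3 | 89.0 | 88.8 |

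Break-even is near a baseline SD of 480, where ρ = 1 - 161²/(2 × 480²) = 0.944.

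**4. If the baseline is wide and ρ is below 0.944,** the change SD must exceed 161. With baseline SD 1,000, change SD = 1,000 × √(2(1 - ρ)); one-sided 0.05:

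| ρ | change SD | truth 0: t-test / adjusted | truth -350: t-test / adjusted |
|---|---|---|---|
| 0.5 | 1,000 | 46.3 / 54.9% | 11.9 / 13.3% |
| 0.7 | 775 | 64.1 / 69.1% | 14.8 / 15.8% |
| 0.8 | 632 | 79.1 / 81.8% | 18.2 / 19.0% |
| 0.9 | 447 | 96.6 / 96.9% | 27.3 / 27.7% |

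**5. Worst case.** The change score is the regression with its slope fixed at 1. Least squares chooses the slope with the smallest residual variance, so the adjusted residual variance cannot exceed the change-score variance, whatever the follow-up variance. The cost is then one degree of freedom plus the imbalance term. With residual SD = change SD = 161, power is 88.6% against 89.4%, a loss of 0.8 points. Over change SDs from 150 to 2,000 at truth 0, the largest loss is 1.04 points (near SD 725).

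**6. Two analyses, one claim** (simulation, 40,000 trials per setting, one-sided 0.05, change SD 161). At truth -350 the two tests give different decisions in 8.8/7.4/5.9/3.6% of trials at ρ = 0.3/0.5/0.7/0.9. At truth -500 each test alone holds about 5%. A claim allowed on either would succeed in 7.3/7.1/6.4/6.1%. The plan does not propose that rule, but it does not rule it out.

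**The case against.** The strongest reply is that nothing here is an error. The t-test is valid under randomization, matches the Section 2.1 endpoint, is the only test with a margin, and has the power claimed. On a natural reading the regression is supportive, and a one-word label would say so.

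The gain may also be nil. At the plan's SD of 161, powers of 93–97% need baseline SDs of only 136–208 steps. The documents suggest a wider spread: eligibility is "Male or female with an age of 18 years or older", both claudication stages qualify, and in the baseline week "the duration and frequency of these extended periods of time will be at" the patient's choosing. With a baseline SD of 500 or more and a change SD of 161, adjustment loses slightly. Recovering a useful gain there means giving up the SD of 161 and moving the truth to 0; at -350 both tests fail and the gain is at most 1.4 points in the table at step 4. The one-point bound also assumes all 40 are analysed at one-sided 0.05. At 0.025 it is 1.2 points; with 15 analysed per arm it is 1.4 (0.05) or 1.7 (0.025), and with 12 it is 1.9 or 2.2.

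All of this stands as qualification. It means that no particular gain can be promised and that the bound on the loss is conditional. It does not remove the asymmetry: the loss stays at or below about 2 points even in those cases, while the gain reaches 8–9 points in some of the cases shown. Nor does it supply the missing role for the regression.

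**Conclusion.** The concern holds, as an improvement to consider and not as a flaw that invalidates the plan. The deciding test ignores a covariate the trial collects and a model it already intends to fit. The effect on power ranges from a loss of about 1 point to a gain of about 8 points at SD 161 (97.1% against 89.4% at ρ = 0.3), and where it falls depends on a baseline SD and a correlation that the documents do not give. These figures assume 20 analysed per arm, one-sided 0.05 and, for the gains, equal variances at baseline and Week 14. The bound on the loss does not need equal variances. Type I error is about 5% for either test taken alone.

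The unstated alpha is a separate gap, which the same edit would close. If the change SD is well above 161, low power at a true difference of -350 is a sample-size matter that adjustment will not repair.

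**What to change.** In Section 6:

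- Make the regression of Week 14 mean daily steps on arm and baseline mean daily steps the single primary non-inferiority analysis. Declare non-inferiority if the lower one-sided 95% confidence bound for the adjusted difference, intervention minus control, lies above -500 steps. One-sided 0.05 is the level consistent with the stated 90% power; if 0.025 is intended, the power statement must be redone.
- Label the t-test on change as supportive, with no claim attached to it.

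The Section 2.1 endpoint need not change, because the adjusted contrast is the same for Week 14 steps and for change. The cost is two sentences and one degree of freedom, with no new data, visits or procedures. If the correlation proves very high there is no gain, and the loss is at most 0.8 power points at SD 161 with all 40 analysed at one-sided 0.05.
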